5.3 Rationale for the Present Study

Although there is evidence of efficacy and safety of solithromycin in adults, the safety and efficacy of solithromycin have not been established in children. There is evidence of similarities in children and adults in 1) CABP definitions and pathophysiology, 2) causative organisms, 3) response to intervention and 4) exposure-response relationship. Therefore, extrapolation of efficacy in pediatric subjects from adult clinical trial efficacy data is reasonable. A safety study in pediatric subjects with CABP, however, is needed to compare the safety and tolerability of solithromycin to comparators. The proposed study will gather necessary safety data and, as a secondary objective, provide an assessment of solithromycin efficacy as CABP treatment in pediatric subjects.

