6 STUDY OBJECTIVES

Primary

- Evaluate the safety and tolerability of solithromycin in adolescents and children with CABP

Secondary

- Evaluate the efficacy of solithromycin in adolescents and children with CABP
- Evaluate the population PK of solithromycin in adolescents and children with CABP

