14.1.2 Sample Size

Subjects will be randomized 3:1 (solithromycin 300: comparator 100), stratified by age, with at least 40 subjects randomized per age group. The sample size of 300 in the solithromycin group is based on the ability to observe an SAE at a frequency higher than 1% (Table 11).

Table 11 Probability of Observing at Least one Subject with a Serious Adverse Event

Number of Subjects	Possible Serious Adverse Event Incidence with 5 Days of Dosing				
	0.1%	0.25%	0.5%	1%	2%
100	0.095	0.22	0.39	0.63	0.87
200	0.18	0.39	0.63	0.87	0.98
300	0.26	0.53	0.78	0.95	>0.99

In addition, this sample size will provide reasonable estimates and 95% CI for safety. If 1 subject has an AE, then the 95% CI (exact binomial) for that AE within the subject population of 300 subjects is 0, 1.8% (see Table 12).

Table 12 Proportion of Subjects with Adverse Events and 95% CI

Number of Events	Proportion	95% CI
0	0	0, 0.012
1	0.003	0.0001, 0.018
2	0.007	0.001, 0.024
3	0.010	0.002, 0.029

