14.1.3 Safety Analysis

For the primary safety endpoints, the frequency and percentage of subjects with AEs and therapy not tolerated will be determined and 95% CIs calculated. Summaries will be calculated by treatment group for the overall safety population and stratified by age group.

Additional safety analyses include summaries of AEs, descriptive statistics of laboratory values, descriptive statistics of vital signs, and frequency distributions of abnormal physical examinations. Laboratory data, such as hematology and serum chemistry data, as well as safety data will be analyzed. Summary statistics for changes from baseline and shift tables will be presented. Continuous laboratory measurements will be described at each visit using descriptive statistics (mean, median, etc.); observed values and changes from baseline will be summarized. Laboratory tests reflective of liver toxicity (e.g., ALT, AST) will be further summarized in terms of the most extreme values and largest changes from baseline (in the appropriate direction) observed from start of study drug through the end of therapy. All analyses will include summaries for both treatment and active comparator.

Additional details of safety analyses will be included in the Statistical Analysis Plan (SAP).

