3.3 Sample Size and Randomization

Approximately 400 subjects ≥ 2 months to 17 years of age inclusive, with CABP will be enrolled. Subjects will be randomized (3:1) into two groups: solithromycin (N~300) or comparator (N~100). Randomization will be stratified by the following age groups:

- Age Group 1: Adolescents from 12 years to 17 years, inclusive
- Age Group 2: Children from 6 years to <12 years
- Age Group 3: Children from 24 months to <6 years
- Age Group 4: Infants from ≥ 2 months to <24 months

A minimum of 40 subjects will be included in each age group. Approximately 20% of subjects will be enrolled in the United States. Enrollment will occur simultaneously for all age groups for which information to inform the dosing regimen is available.

The sample size of 300 in the solithromycin group is based on the ability to observe an SAE at a frequency higher than 1% (see Table 1).

Table 1 Probability of Observing at Least 1 Subject with a Serious Adverse Event

Number of subjects	Possible Serious Adverse Event Incidence with 5 Days of Dosing				
	0.1%	0.25%	0.5%	1%	2%
100	0.095	0.22	0.39	0.63	0.87
200	0.18	0.39	0.63	0.87	0.98
300	0.26	0.53	0.78	0.95	>0.99

In addition, this sample size will provide reasonable estimates and 95% confidence interval (CI) for safety. If 1 subject has an AE, then the 95% CI (exact binomial) for incidence of that AE within the subject population of 300 subjects is 0.01%, 1.8% (see Table 2).

Table 2 Proportion of Subjects with Adverse Events and 95% CI

Number of events	Proportion	95% CI
0	0	0, 0.012
1	0.003	0.0001, 0.018
2	0.007	0.001, 0.024
3	0.010	0.002, 0.029

The above estimates assume that all 300 subjects assigned to the solithromycin arm will be evaluable for safety and do not account for the possibility that a subject may be excluded from the safety analysis, for example because she/he did not receive any study drug, or withdrew consent prior to completing follow up evaluations for safety.

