10.2 Primary Safety and Tolerability Endpoints

Primary safety endpoints will be the proportion of subjects in the safety population experiencing a TEAE and the proportion of subjects in the safety population discontinuing study drug due to a related AE. Discontinuation from related AE counts will be created by using any discontinuation from related AE documented in the study drug discontinuation page and the AE data for a subject. The first safety endpoint will be evaluated through the Day 28 visit (28 days ± 4 days after randomization). This will be a composite of TEAEs through Day 16 visit and TESAEs through Day 28 visit. The second safety endpoint will be evaluated through the last day of study drug dosing.

For the primary safety end points, the frequency and percentage of subjects with at least one treatment emergent adverse event, and the frequency and percentage of subjects discontinuing study drug due to a related AE, will be determined. Ninety-five percent Clopper-Pearson (exact) confidence intervals will be calculated for each incidence of occurrence by treatment arm. Summaries will be calculated by treatment arm for the overall safety population, by treatment arm stratified within age group, and within age group and formulation for the solithromycin arm. Patient-level information for adverse events and subjects discontinuing study drug due to a related AE will be listed. For this analysis subjects will be grouped according to their randomized treatment arm assignment (intent-to-treat analysis).

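### The stated rationale is a safety comparison with comparators, but no between-arm estimate is planned for either primary safety endpoint

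*SAP*

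**What the plan says.** Protocol 5.3 gives the reason for the trial: "A safety study in pediatric subjects with CABP, however, is needed to compare the safety and tolerability of solithromycin to comparators". The synopsis repeats this. The primary objective in Protocol 6 and SAP 3.2 is narrower: "Evaluate the safety and tolerability of solithromycin in adolescents and children with CABP". On design, Protocol 14.1.2 states: "Subjects will be randomized 3:1 (solithromycin 300: comparator 100), stratified by age".

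The primary safety endpoints are the proportion of subjects with a TEAE and the proportion who stop study drug because of a related AE. SAP 10.2 plans counts, percentages and exact intervals, and says that "confidence intervals will be calculated for each incidence of occurrence by treatment arm". These are tabulated by arm, by arm within each age group, and by age group and formulation for solithromycin. Protocol 14.1.3 likewise plans frequencies with 95% intervals, and adds: "All analyses will include summaries for both treatment and active comparator".

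No difference, ratio or age-adjusted contrast for either endpoint appears in Protocol 14.1, in SAP 10, or in the output titles in SAP 12 (titles only; the shells are not in the text supplied). Protocol 14.1.5 and SAP 10.4 say the study is not powered to compare efficacy between groups. Nothing similar is said about safety.

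**The concern.** The comparator arm exists, on the protocol's own account, so that safety can be compared. The quantity that expresses the comparison is the difference between the arms with its interval, and this is not planned. The reader gets two one-sample intervals side by side. Neither describes the uncertainty of the difference, and setting one against the other by eye is a conservative substitute. In a safety trial that mistake leans toward false reassurance, because an excess of adverse events can sit behind overlapping intervals.

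Early termination does not explain the gap. SAP version 1.1 was curtailed after the trial stopped, but Protocol 14.1.3 was written for 400 subjects and plans no contrast either.

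**Working it through.** **Inputs from the documents.** Planned arms 300 and 100 (Protocol 14.1.2). Enrolment below one quarter of 400 (SAP 2), so fewer than 100 subjects; at 3:1 that is at most about 75 and 25. Two-sided 95% Clopper-Pearson intervals per arm (SAP 10.2).

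**Assumed inputs.** The documents give no expected pediatric rates. I take 40% TEAE on comparator with a range of 20% to 50%, and 2% to 5% for stopping because of a related AE.

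**Step 1: the plan's own figures.** Protocol Table 11 uses 1 − (1 − p)^n. At n = 300 and p = 1% this is 1 − 0.99^300 = 0.951, and the table has 0.95. Table 12 uses Clopper-Pearson intervals at n = 300. One event gives 0.0001 to 0.0184, and the table has 0.0001 to 0.018. Both tables reproduce. Both concern one arm only.

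**Step 2: precision of the missing estimate.** With a common rate p, the 95% half-width of the risk difference is 1.96 × √[p(1 − p)(1/n₁ + 1/n₂)]. At p = 0.40:

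- 300:100: 1.96 × √[0.24 × (1/300 + 1/100)] = 0.111
- 75:25: 1.96 × √[0.24 × (1/75 + 1/25)] = 0.222

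| Assumed rate | 300:100 | 75:25 |
|---|---|---|
| TEAE 20% | ±9.1 points | ±18.1 points |
| TEAE 30% | ±10.4 | ±20.7 |
| TEAE 40% | ±11.1 | ±22.2 |
| TEAE 50% | ±11.3 | ±22.6 |
| Related-AE stop 2% | ±3.2 | ±6.3 |
| Related-AE stop 5% | ±4.9 | ±9.9 |

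The normal approximation is rough in the last two rows. With 0/75 against 0/25, the Newcombe interval for the difference runs from −13.3 to +4.9 points.

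**Step 3: what separate intervals hide (comparator at 40%).** The Clopper-Pearson limits are the 2.5% quantile of Beta(x, n − x + 1) and the 97.5% quantile of Beta(x + 1, n − x).

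- *300:100.* Comparator 40/100 has interval 30.3% to 50.3%. The solithromycin interval first clears it at 169/300, a difference of 16.3 points. The difference interval excludes zero from 154/300: difference 0.1133, half-width 1.96 × √(0.5133 × 0.4867/300 + 0.24/100) = 0.1114, lower limit +0.0019.
- *75:25.* Comparator 10/25 has interval 21.1% to 61.3%. The solithromycin interval first clears it at 55/75, a difference of 33.3 points. The difference interval excludes zero from 47/75: difference 0.2267, half-width 1.96 × √(0.6267 × 0.3733/75 + 0.24/25) = 0.2210, lower limit +0.0056.

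Wald, Newcombe and Miettinen-Nurminen intervals give the same thresholds.

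**Step 4: two worked cases.**

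- 126/300 against 30/100: the per-arm intervals of 36.4% to 47.8% and 21.2% to 40.0% overlap. The difference is +12.0 points, Newcombe 95% CI +1.0 to +21.9.
- 50/75 against 10/25: the per-arm intervals of 54.8% to 77.1% and 21.1% to 61.3% overlap. The difference is +26.7 points, Miettinen-Nurminen 95% CI +4.2 to +46.6.

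**The case against.** The strongest reply is that the planned analysis fits the objective as written. The objective names solithromycin only, the endpoints are proportions, and the sample size rests on seeing a rare SAE among 300 solithromycin subjects. One-sample exact intervals suit that. With both arms tabulated side by side, anyone can subtract and work out a crude interval. With fewer than 100 subjects the contrast will be imprecise in any case.

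Much of this stands, and it rules out three stronger conclusions that a reader might draw.

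- *That the stratification is ignored.* It is not. SAP 10.2 and Table 14.4.1 report by arm within the age groups that define the randomisation strata. Only a contrast that uses the strata is missing.
- *That the primary question goes unanswered.* The comparative wording is in the rationale, not in the objective.
- *That the plan judges the arms by interval overlap.* No such rule exists. The overlap thresholds above describe a mistake a reader could make. By that rule the arms would first look different at z = 2.88 (300:100) or 3.02 (75:25), that is p of about 0.004 and 0.003, but this is not an operating characteristic of the plan.

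The reply does not show that the promised comparison is reported. A crude subtraction by the reader is neither pre-specified nor age-stratified. Rewording the rationale would remove the inconsistency on paper but would still leave the randomised comparison unreported. Small numbers are a reason to show the uncertainty of the difference.

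**Conclusion.** The point holds as a mismatch between rationale and analysis. The trial is justified by a comparison and randomised to support one, yet neither document plans an estimate of it for the primary safety endpoints. No power or error-rate statement is wrong.

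At a 40% TEAE rate the contrast would have been known to about ±11 points at the planned size, and to about ±22 points at best at the enrolled size. Over 20% to 50% this becomes 9 to 11 and 18 to 23 points. A reader relying on overlap would miss observed differences from about 11 up to 16 points (300:100), or from about 23 up to 33 points (75:25), that a difference interval would separate from zero.

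These sizes rest on the assumed rates and unstratified intervals, and on 75:25 as an upper bound for enrolment. For related-AE discontinuation the estimate may say little if events are few.

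**What to change.** In SAP 10.2 and Table 14.4.1, add the solithromycin-minus-comparator risk difference with a 95% Miettinen-Nurminen interval for both primary safety endpoints, in the safety population by randomised arm. Stratify by the two consolidated age groups of SAP 5.1 where counts allow, and leave the estimate unstratified otherwise. The four randomisation groups are too thin now: 25 comparator subjects over four strata is about six each. Label the row descriptive, without a test, and added after termination. SAP 2 already allows added analyses on those terms.

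The cost is one sentence and one table row per endpoint, with no new data. The downside is that the intervals will be wide, and uninformative for related-AE discontinuation if counts are near zero.

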10.3 Additional Safety Analyses

Additional safety analyses include summaries of AEs, descriptive statistical summaries of abnormal laboratory values, frequency distributions and shift tables summarizing abnormal laboratory values, graphs of lab values and vital signs, and summaries of concomitant medications as well as prior medications. Pregnancy test results and non-pharmacological treatments will be listed but not summarized. These analyses will be presented in the safety population using intent-to-treat analysis. Summaries will be produced by treatment arm, drug route, and consolidated age groups (2 months - <6 years, 6 years – 17 years inclusive) with the exception of lab graphs and

shift tables. The lab graphs and shift tables will be summarized by treatment arm, with all age groups combined. Safety data will also be listed by treatment arm, age group, formulation (for solithromycin patients only), and subject, with relevant information such as values, normal ranges, and severity presented.

10.3.1 Adverse Events

AEs (as defined in section 12.1 of Protocol) will be collected from the time of signing the informed consent and assent (if applicable) through 16 days (± 4 days) after randomization. SAEs will be collected through 28 days (± 4 days) after randomization. AEs will be tabulated by using the Medical Dictionary for Regulatory Activities (MedDRA v18.1) system organ class and preferred term. The treatment emergent adverse event (TEAE) is defined as any AE that has an onset on or after the first dose of either study drug, or any pre-existing AE that increases in severity after dosing with either study drug. Adverse events will be tabulated to show the number of subjects with at least one AE, number of subjects with at least one TEAE, and the number of subjects that experienced each individual count of AEs and TEAEs (e.g., number of subjects with 2 AEs, number of subjects with 3-4 AEs, etc.). Additional summaries will be created for infusion site events as well as TEAEs excluding these infusion site events.

10.3.2 Laboratory Data

Descriptive statistics will be generated for post-baseline abnormal laboratory data, such as hematology and serum chemistry values. Additionally, shift tables will be presented. The shift tables tabulate the number of lab values determined to be “Normal” and “Abnormal” at baseline and post-baseline timepoints. The classifications on shift tables will categorize lab values as “Normal” when they are in an acceptable range, using a combination of clinician judgment specific to each lab test, and the local lab reference ranges (see below). Laboratory values outside the normal range will be graded on the Labs Listing as 1x, 2x, 3x, 5x or 10x the upper limit (or .5x, 1x the lower limit) of normal value based on appropriate increases or decreases. Lab tests reflective of liver toxicity (ALT, AST, and Total and Direct Bilirubin) will be further summarized in terms of the most extreme values and largest increases from baseline observed from the start of study drug through Day 16 Post-Randomization (± 4 days). Laboratory data will also be summarized graphically to show the magnitude and changes in individual subject values over time relative to normal ranges.

Laboratory Name	Clinically Pertinent Normal Range
Blood Urea Nitrogen [BUN]	(0, Site Specific ULN)
Calcium	(Site Specific LLN, Site Specific ULN)
Serum Creatinine	(0, Site Specific ULN)
Potassium	(Site Specific LLN, Site Specific ULN)
Sodium	(Site Specific LLN, Site Specific ULN)

AST	(0, Site Specific ULN)
ALT	(0, Site Specific ULN)
Alkaline Phosphatase	(0, Site Specific ULN)
Total Bilirubin	(0, Site Specific ULN)
Direct Bilirubin	(0, Site Specific ULN)
Albumin	(Site Specific LLN, ∞)
Hemoglobin	(Site Specific LLN, ∞)
Hematocrit	(Site Specific LLN, ∞)
WBC Count	(Site Specific LLN, Site Specific ULN)
Platelet Count	(Site Specific LLN, Site Specific ULN)
Neutrophils	(Site Specific LLN, Site Specific ULN)
Lymphocytes	(Site Specific LLN, Site Specific ULN)
Monocytes	(Site Specific LLN, Site Specific ULN)
Eosinophils	(Site Specific LLN, Site Specific ULN)
Basophils	(Site Specific LLN, Site Specific ULN)
C-reactive protein	(0, Site Specific ULN)
Procalcitonin	(0, Site Specific ULN)

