In the Phase 3 IV to oral CABP study, 5 (1.2%) patients in the solithromycin group and 7 (1.6%) patients in the moxifloxacin group died during the study. None of the SAEs resulting in death was considered related to study drug. A total of 30 (6.9%) patients in the solithromycin group and 23 (5.4%) patients in the moxifloxacin group reported at least 1 non-fatal SAE. Only 3 SAEs were considered related to study drug by the investigators (urticaria and anaphylactic reaction in 1 patient each in solithromycin and anaphylactic reaction in 1 moxifloxacin patient). The most frequently reported infusion site related TEAEs were infusion site pain (10.4%), infusion site phlebitis (10.0%) and infusion related reaction (6.5%). Infusion site related TEAEs were mostly mild or moderate in intensity and infrequently led to discontinuation of study drug or withdrawal from the study (in 1 moxifloxacin and 10 solithromycin patients). Apart from infusion site related events, the most common AEs observed in patients receiving solithromycin were diarrhea (5.9%) and headache (4.2%).

In the adolescent oral phase 1 study (CE01-119), 12 AEs were reported, of which 9, including 1 SAE (limb abscess), were unrelated to solithromycin. Three subjects had AEs related to study drug: 2 separate episodes of mild headache and 1 episode of increased transaminases ($<3\times$ ULN).

The most common AEs reported after multiple IV doses were general disorders and administrative site conditions (infusion-related pain) followed by nervous system disorders and vascular disorders (phlebitis), with the majority mild in severity.

Solithromycin, like most antibiotics and like all macrolide antibiotics, has been associated with hepatic aminotransferase elevations. In the pooled Phase 3 CABP trials, ALT elevations to $>3\times\text{ULN}$, $>5\times\text{ULN}$ and $>10\times\text{ULN}$ were seen in 7.2%, 2.4% and 0.1% of solithromycin recipients compared to 3.6%, 1.0% and 0.2% of moxifloxacin recipients. Elevations of ALT to $>3\times\text{ULN}$ were 5.4% in the oral study and 9.1% in the IV to oral study. These elevations were typically asymptomatic, not associated with bilirubin elevation and readily reversible, with improvement in many cases seen during continued dosing. There have been no Hy's Law cases.

Multiple lines of evidence point to an exposure-response relationship for ALT elevation with solithromycin.

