8.2 Exclusion Criteria

1. Confirmed or suspected respiratory-tract infection attributable to sources other than community-acquired bacterial pathogens (e.g., ventilator-associated pneumonia; hospital-acquired pneumonia).
2. Received > 48 hours of potentially effective systemic antibacterial therapy for CABP immediately prior to randomization (exception: clinical or microbiological treatment failure or progression of signs or symptoms of CABP as determined by the investigator).
3. Confirmed or suspected bacterial meningitis.
4. Known active tuberculosis.
5. Non-infectious causes of pulmonary infiltrates (e.g., cystic fibrosis, chemical pneumonitis from aspiration, hypersensitivity pneumonia).
6. Evidence or history of clinically significant medical condition that may, in the assessment of the investigator, impair study participation or pose a significant safety risk or diminish the subject's ability to undergo all study procedures and assessments.
7. Hepatic dysfunction evidenced by ALT or AST > 3 times ULN or direct bilirubin greater than 2 times ULN (if direct bilirubin values are not available in a time frame consistent with enrollment requirements, total bilirubin must be < 2 times ULN).
8. Treatment with the following drugs within 72 hours prior to first dose of study drug or expected to receive these drugs during the treatment phase: drugs that potently inhibit CYP3A4 (nefazodone, fluconazole, ketoconazole, conivaptan, diltiazem, verapamil, aprepitant, imatinib, protease inhibitors, clarithromycin, ciprofloxacin, erythromycin, itraconazole, mibefradil, posaconazole, telithromycin, and voriconazole); CYP3A4 inducers (rifampin, rifabutin, phenytoin, fosphenytoin, carbamazepine, phenobarbital, rufinamide, modafinil, armodafinil, etravirine, efavirenz, nevirapine, rilpivirine, bosentan, troglitazone, pioglitazone,

and St. John's wort). In addition, the following drugs may not be co-administered with solithromycin in this trial due to the potential for adverse drug-drug interaction: digoxin, colchicine, midazolam, quinidine, ergotamine, dihydroergotamine, rivaroxaban, apixaban, dabigatran, edoxaban, cisapride, cyclosporine, sildenafil, astemizole, and alfentanil.

9. Breast-feeding females.
10. Positive pregnancy test in females of childbearing potential.
11. History of anaphylaxis to macrolide antibiotics.
12. Previous participation in this study.

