14.4 Safety Data

Table 14.4.1	Proportion of Subjects Experiencing a Treatment Emergent Adverse Event or Discontinuing Study Drug Due to Related Adverse Event – By Treatment Arm and Age Group
Table 14.4.1.1	Proportion of Subjects Experiencing a Treatment Emergent Adverse Event or Discontinuing Study Drug Due to Related Adverse Event – By Treatment Arm, Age Group, and Formulation
Table 14.4.2	Overview of Adverse Events – By Treatment Arm, Consolidated Age Group, and Drug Route
Table 14.4.2.1	All Treatment Emergent Adverse Events by System Organ Class and Preferred Term – By Treatment Arm, Consolidated Age Group, and Drug Route
Table 14.4.2.1.1	Treatment Emergent Adverse Events by System Organ Class and Preferred Term, Excluding Infusion Site Adverse Events – By Treatment Arm, Consolidated Age Group, and Drug Route
Table 14.4.2.1.2	Treatment Emergent Infusion Site Adverse Events by System Organ Class and Preferred Term – By Treatment Arm, Consolidated Age Group, and Drug Route
Table 14.4.2.2	Overview of Serious Adverse Events – By Treatment Arm, Consolidated Age Group, and Drug Route
Table 14.4.2.3	Treatment Emergent Serious Adverse Events by System Organ Class and Preferred Term – By Treatment Arm, Consolidated Age Group, and Drug Route

Table 14.4.3	Shift from Baseline to Worst Post-Baseline Value: Hematology Tests – By Treatment Arm
Table 14.4.3.1	Abnormal Laboratory Results Summary: Hematology Tests – By Treatment Arm
Figure 14.4.3.2	Worst Post-Baseline vs Baseline Laboratory (Scaled by Normal Values): Hematology Tests – By Treatment Arm
Figure 14.4.3.3	Worst Post-Baseline vs Baseline Laboratory (Scaled by Normal Values): Hematology Tests – By Solithromycin Consolidated Age Group and Drug Formulation
Table 14.4.3.2	Shift from Baseline to Worst Post-Baseline Value: Chemistry Tests – By Treatment Arm
Table 14.4.3.2.1	Abnormal Laboratory Results Summary: Chemistry Tests – By Treatment Arm
Figure 14.4.3.2.2	Worst Post-Baseline vs Baseline Laboratory (Scaled by Normal Values): Chemistry Tests – By Treatment Arm
Figure 14.4.3.2.3	Worst Post-Baseline vs Baseline Laboratory (Scaled by Normal Values): Chemistry Tests – By Solithromycin Consolidated Age Group and Drug Formulation
Table 14.4.3.2.4	Summary of Liver Function Tests – By Treatment Arm
Table 14.4.3.2.5	Summary of Liver Function Tests – By Solithromycin Consolidated Age Group and Drug Route
Figure 14.4.4	Summary Plot of Vital Signs – By Treatment Arm

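### The chemistry shift table has only Normal and Abnormal, so for liver tests it cannot show how far a value rose, and the SAP text commits to no by-arm count above any ULN multiple

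*SAP*

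**What the plan says.** **Shift tables.** SAP 10.3.2: "The shift tables tabulate the number of lab values determined to be" Normal or Abnormal, at baseline and afterwards. Normal is set "using a combination of clinician judgment specific to each lab test, and the local lab reference ranges", and the range list in the same section gives ALT and AST as ("0, Site Specific ULN"). The output list in SAP section 12 names Table 14.4.3.2, "Shift from Baseline to Worst Post-Baseline Value: Chemistry Tests", by treatment arm.

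**Grades.** SAP 10.3.2 also says: "Laboratory values outside the normal range will be graded on the Labs Listing as 1x, 2x, 3x, 5x or 10x the upper limit". SAP section 11 plans a table of laboratory abnormalities and grade for the interim DMC reviews.

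**Liver summary.** ALT, AST and total and direct bilirubin are to be "further summarized in terms of the most extreme values and largest increases from baseline", from the start of study drug through Day 16 (±4). Tables 14.4.3.2.4 (by arm) and 14.4.3.2.5 (solithromycin, by consolidated age group and route) are listed for liver function tests.

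**Eligibility.** Protocol 8.2, criterion 7, excludes "Hepatic dysfunction evidenced by ALT or AST > 3 times ULN". A baseline above 1x and up to 3x ULN is admissible.

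**Known signal.** Protocol 5.2.4.1 reports that in the pooled adult Phase 3 trials ALT elevations above 3x, 5x and 10x ULN "were seen in 7.2%, 2.4% and 0.1% of solithromycin recipients", against 3.6%, 1.0% and 0.2% on moxifloxacin. It also describes an exposure-response relationship for ALT.

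**The concern.** Safety is the primary objective, and raised ALT is a known, exposure-related effect of the drug. The adult programme expressed that effect as the share of patients above 3x and 5x ULN. A table cut once, at 1x ULN, merges exactly those categories.

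The adverse event tables may not make up for this. Protocol 12.1 does not count a laboratory abnormality as an AE unless it comes with signs or symptoms or needs intervention; one that leads to interruption or discontinuation of study drug will usually count. Protocol 5.2.4.1 describes the adult elevations as typically asymptomatic. Many such rises would therefore stay out of the primary TEAE endpoint, leaving the laboratory tables to carry the comparison between arms. If those tables do not count children above a given ULN multiple, the paediatric result cannot be set directly beside the adult one.

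**Working it through.** The plan states no figure to reproduce here. The check applies the SAP's rule to example values.

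**Inputs**
- Shift category: Normal if ALT is at or below 1x site ULN, otherwise Abnormal (SAP 10.3.2).
- Listing grade: highest of 1x, 2x, 3x, 5x, 10x ULN reached (SAP 10.3.2).
- Admissible baseline: up to 3x ULN (Protocol 8.2).

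| Baseline (x ULN) | Worst post-baseline (x ULN) | Shift-table cell | By listing grade |
|---|---|---|---|
| 0.9 | 1.1 | Normal to Abnormal | normal to 1x |
| 0.9 | 10 | Normal to Abnormal | normal to 10x |
| 1.1 | 1.2 | Abnormal to Abnormal | 1x to 1x |
| 1.1 | 10 | Abnormal to Abnormal | 1x to 10x |
| 2.9 | 10 | Abnormal to Abnormal | 2x to 10x |
| 3.0 | 5.1 | Abnormal to Abnormal | 3x to 5x |

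The first two rows share a cell, and so do the last four. The SAP's own grades separate all the large rises from the trivial ones.

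**Illustrative size.** Assume that the adult rates above 3x ULN apply to children (expected number = rate × n).
- Planned size: 0.072 × 300 = 21.6 on solithromycin; 0.036 × 100 = 3.6 on comparator.
- Terminated size: SAP section 2 gives final enrolment as fewer than one quarter of 400, that is, below 100. Taking 75 and 25 as a ceiling at 3:1: 0.072 × 75 = 5.4; 0.036 × 25 = 0.9.

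These counts cover children of any baseline status. The documents do not say how many start above 1x ULN, so the number in the Abnormal-to-Abnormal cell cannot be estimated.

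**What the other outputs commit to**
- Liver summary: extreme values and largest increases. No ULN threshold is named, alkaline phosphatase is absent, and it ends at Day 16 (±4). SAP 10.1 says liver tests are also sought at Day 28. Protocol 5.2.4.1 reports adult alkaline phosphatase above 1.5x ULN in 5.2% vs 2.9%.
- Figures 14.4.3.2.2 and 14.4.3.2.3: worst against baseline, scaled by normal values. These show individual points, not proportions.
- Table 14.4.3.2.1: summary of abnormal chemistry results by arm, with no grading stated.
- DMC table: graded, but for interim review.

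**The case against.** The strongest reply is that the SAP already has an analysis for this purpose. A child going from 1.1x to 10x ULN contributes to the extreme-value and largest-increase summary by arm, and appears in the scaled plot and the graded listing. With fewer than 100 children and descriptive analyses, the few points above 3x ULN could be counted by eye, and a finely graded grid would be mostly empty. Only table titles are visible, so it cannot be shown that Tables 14.4.3.2.1 and 14.4.3.2.4 lack ULN rows.

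Most of this stands, and it limits the point. A reader might infer one of three stronger claims, and the documents support none of them:
- That the analysis as a whole would miss a large ALT rise. The liver summary, plots and listing would show it.
- That the grades are used only in a listing. The DMC table uses grade as well.
- That about 22 vs 4 children would be hidden. That count covers all baselines, and a child who starts normal does register as a shift; only the size of the rise is lost.

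Two things remain. The text for final reporting does not commit to a proportion by arm above any ULN multiple. Also, the weekly and quarterly liver checks in Protocol 12.1.3 do not close the gap for children with a raised baseline: apart from the Hy's Law criterion, their 2x and 3x ULN triggers require a normal baseline. The DMC does receive all liver test data twice a year.

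**Conclusion.** The limitation is real but confined to how results are tabulated. For liver tests, Table 14.4.3.2 cannot separate a rise to 1.1x from a rise to 10x ULN, and it cannot show worsening in a child enrolled between 1x and 3x ULN. This follows from the SAP's range list, which fixes the ALT and AST limit at site ULN; the reference to clinician judgment does not alter that entry. No signal is lost from the data or from every output. What is missing is a stated commitment to report n and percent by arm above ULN multiples, together with alkaline phosphatase and Day 28 values in the liver summary.

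If the adult rates carried over, the children concerned above 3x ULN would number about 22 vs 4 at the planned size, and at most about 5 vs 1 at the final size. Both are illustrations that rest on the adult rates, and the second also on an assumed 75:25 split. This is a low-cost improvement to the reporting of a known hazard, not an error that undermines the safety analysis.

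**What to change.** For ALT, AST, alkaline phosphatase and total and direct bilirubin, tabulate baseline category by worst post-baseline category, by arm, using the ULN multiples already graded in SAP 10.3.2. Collapse sparse categories where needed, for example ≤1, >1–3, >3–5 and >5x ULN. Give n and percent, with children tested as the denominator. Put the same rows in Table 14.4.3.2.4, add alkaline phosphatase to it, and extend its window to include the Day 28 tests.

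The cost is a change to table shells and programming; the grades are already planned and no new data are needed. The downside is some sparse cells at the final sample size. Collapsing limits this: because ALT and AST above 3x ULN are excluded at entry, only two baseline rows should be occupied for those tests, so 2 × 4 = 8 cells per arm.
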